6.4 Covariates and Subgroups

This study is not powered to perform formal subgroup analyses. Age stratum (18-40, 41-60 years) and site will be used to define subgroup analyses for descriptive purposes.

6.5 Missing Data

Imputation of missing values is not planned. Imputation may be implemented for secondary or tertiary outcomes if supported by the data and if sufficient consequence to justify their inclusion.

6.6 Interim Analyses and Data Monitoring

The PSRT will review safety data routinely throughout the study. The NIAID Intramural DSMB will provide an independent safety review at scheduled intervals to coincide with their biannual meeting schedule.

Interim analyses are mentioned above in **Section 6.2** and are also covered and detailed elsewhere in the VRC 704 Interim Analysis Plan dated 19 January 2018.

Note that these analyses will not be used for early trial termination. Therefore, final p-values will not be adjusted for interim analyses.

6.7 Multicenter Studies

Data will be pooled across all clinical sites. Center effects are not anticipated because the sites are using standardized procedures for vaccination and assessment of solicited and unsolicited adverse events, and the study relies on central laboratories for the assessment of immunogenicity and clinical efficacy endpoints.

Nevertheless, to guard against the potential for regional differences, the primary analysis will also be presented by site.

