4.5.2 Method of Assigning Subjects to Treatment Groups (Randomization)

For each clinical site, randomization will be 1:1 allocation within each stratum of age group to either the CHIKV VLP vaccine or PBS placebo. The randomization sequence was generated in SAS using permuted blocked randomization with randomly selected block sizes of two or four.

Randomizations will be done online using an electronic randomization system. The randomization code was prepared by the Protocol Statistician and included in the enrollment module for the trial. The randomization code will link to the treatment assignment. To decrease the potential for subject dropouts during the period between randomization and initial injection, the electronic data system will assign each subject a randomization code on Day 0 after confirmation of eligibility to begin Day 0 study injections has been entered into the system. Manual randomization back-up procedures and instructions will be provided for use in the event that the site temporarily loses access to the Internet or the online enrollment system is unavailable to a study site.

If an individual is screened but does not enroll into the clinical trial, screening records will be kept to document the reason the individual did not enroll.

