9 IMMUNOGENICITY EVALUATION

Specimens to evaluate immunogenicity will be taken at baseline and at specified time points. The primary immunogenicity timepoint is 4 weeks after the second injection. Measurements of CHIKV-specific humoral immune responses will be assessed by neutralization antibody (NAb) assays. A listing of individual titer levels and the corresponding planned and actual collection dates are presented in **Appendix III, Listing 16.2.6**.

At some sites, positive baseline Week 0 neutralization antibody assay results were reported. ELISA response data, captured as part of the screening eligibility process, have been received by the Sponsor from the laboratory. When raw ELISA data is received, baseline ELISA responses will be assessed in relation to neutralization antibody data and results will be reported. For further information, a separate analysis plan will be created to elaborate on specific analyses to be performed.

The principle immunogenicity endpoint is measured at Week 8 by neutralization assay.

Descriptive analyses will be presented by study day, age group, and treatment group, aggregated over all study sites and by site. If none or a very small number of placebo group subjects have a neutralization response, their results will only be reported for the positive response rate summaries and omitted from other analyses. This approach is taken to achieve brevity and easier understanding of results when the control group has no meaningful responses.

Summaries include:

- GMT and their confidence intervals (**Table 14.2.1, Appendix I**)
- Geometric mean ratio (GMR) of results obtained at baseline (Week 0) to results obtained at Week 8 and its 95% CI. (**Table 14.2.1, Appendix I**)
- Positive response rates, as defined by an assay-specific post dose response, and their exact 95% CI (**Table 14.2.1, Appendix I**)
- Reverse cumulative distribution of the neutralization assay results (**Figure 14.2.1, Appendix II**)
- Boxplots of titer values (**Figure 14.2.2, Appendix II**).

These summaries will be repeated for all exploratory research tests used to measure exploratory immunogenicity endpoints at the timepoints for which there are data.

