Pulse	Normal													
	Mild													
	Moderate													
	Severe													
	Potentially Life Threatening													
Temperature (°C)	Normal													
	Mild													
	Moderate													
	Severe													
	Potentially Life Threatening													

TABLE 14.3.6:
Number and Percentage of Subjects with Concurrent Medications by
Treatment Group <<Age Stratum>>

Medication	CHIKV (N=X)		Placebo (N=X)		All Subjects (N=X)	
	n	%	n	%	n	%
	x	x.x	x	x.x	x	x.x

TABLE 14.3.7:
Number of Pregnancies by Outcome and Treatment Group

	CHIKV (N=X)	Placebo (N=X)	All Subjects (N=X)
Total pregnancies	x	x	x
Live births			
Spontaneous abortions			
Elective abortions			
Ectopic pregnancies			
Stillbirths			

TABLE 15.1.1:
Incidence of Clinical Cases of CHIKV Post Dose One by Treatment Group and Stratified by Age

Age Stratum	CHIKV			Placebo		
	n	%	95%CI	n	%	95%CI
18-40	x	xx	xx-xx	x	xx	xx-xx
41-60						
Aggregate (18-60)						

Note: Subjects not receiving dose two are included in this table.
 n = number of subjects with CHIKV symptoms (clinical cases)
 % = n divided by the number of subjects receiving dose one
 95%CI = 95% Clopper-Pearson confidence interval.

TABLE 15.1.2:
Incidence of Clinical Cases of CHIKV Post Dose Two by Treatment Group and Stratified by Age

Age Stratum	CHIKV			Placebo		
	n	%	95%CI	n	%	95%CI
18-40	x	xx	xx-xx	x	xx	xx-xx
41-60						
Aggregate (18-60)						

n = number of subjects with CHIKV symptoms (clinical cases)

% = n divided by the number of subjects receiving dose two and free of infection when receiving dose two

95%CI = 95% Clopper-Pearson confidence interval.

Additional Tables using the same format as 15.1.1 and 15.1.2

TABLE 15.1.3:
Incidence of PCR Confirmed Cases of CHIKV Post Dose One by Group and Stratified by Age

TABLE 15.1.4:
Incidence of PCR Confirmed Cases of CHIKV Post Dose Two by Group and Stratified by Age

TABLE 15.2.1:

Primary Exploratory Analysis – Vaccine Efficacy for Time to Occurrence of Clinical CHIKV Infection Post Dose One

	CHIKV N= Placebo N=		
	V.E.	95% CI for V.E.	p-value
Primary Analysis: Unadjusted	x.xx	xx.xx - xx.xx	x.xxx

N=number of subjects in the specific treatment group that received first dose

V.E. =Vaccine efficacy obtained from Cox Proportional Hazard model

95%CI = 95% confidence interval obtained from Cox Proportional Hazard model

p-value = result of comparison of Kaplan-Meier survival curves between groups by Log-rank test.

TABLE 15.2.2:

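### The reason SAP 6.7 gives for pooling sites does not cover exposure or prior immunity, and the lead efficacy and NAb comparisons do not use the site-by-age strata of the randomisation

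*Combined protocol and SAP*

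**What the plan says.** **Pooling.** SAP 6.7 states: "Data will be pooled across all clinical sites". Its reason follows: "Center effects are not anticipated because the sites are using standardized procedures for vaccination and assessment". It also cites reliance on central laboratories. It then adds a safeguard: "Nevertheless, to guard against the potential for regional differences, the primary analysis will also be presented by site".

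**Randomisation.** SAP 4.5.2: "For each clinical site, randomization will be 1:1 allocation within each stratum of age group", using "permuted blocked randomization with randomly selected block sizes of two or four". The table shells show six sites and two age groups, so there are 12 strata.

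**Efficacy (exploratory).** SAP 10.2 makes the vaccine-placebo comparison by Cox model and log-rank test the principal exploratory analysis. The shells for Tables 15.2.x label it "Primary Analysis: Unadjusted". In the SAP 10.3 log-rank code the only STRATA variable is treatment, which is the factor being compared. A secondary exploratory analysis adjusts for age and site in the text of 10.2, and for age, race and site in Tables 15.3.x.

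**NAb.** Table 14.2.1 has p-values for Week 8 GMT, geometric mean ratio (GMR) and response rate, overall and by site, and repeated by age stratum. Fisher's exact test is named for response rates. No test is named for GMT or GMR.

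**Baseline antibody.** SAP 9: "At some sites, positive baseline Week 0 neutralization antibody assay results were reported". Further analysis of this is left to a separate plan.

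**The concern.** The argument in SAP 6.7 concerns how subjects are vaccinated and measured. Sites can follow identical procedures and still differ in mosquito-borne transmission and in how many subjects were exposed before. SAP 9 records positive baseline results at some sites in the very quantity that is the secondary endpoint, although a negative CHIKV screening antibody result was an entry criterion. The stated reason therefore does not support leaving site out.

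Blocking within site and age makes the arms more alike than simple randomisation would. An analysis that ignores the blocking leaves between-site variation in the error term, so standard errors are too large and test size falls below nominal. The protocol (6.3) says the trial is meant to inform Phase 3 through estimates of incidence and vaccine effects. Over-wide intervals work against that purpose even though no formal hypothesis is tested.

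The safeguards cover this only in part. By-site rows show heterogeneity without using it in a pooled comparison, and the efficacy shells (Tables 15.1.x and 15.2.x) have no site rows; Table 14.1.4 gives infection status by site. The GMR is a within-subject measure and so takes some account of baseline titre, but the Week 8 GMT and response-rate comparisons do not.

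**Working it through.** **1. The plan's own precision figure.** SAP Table 4 (protocol Table 5) gives a 95% CI for the vaccinee GMT with n = 180, log mean 7.41 and log SD 0.70.

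exp(7.41 ± t(0.975, 179 df) × 0.70/√180) = (1490.8, 1831.6), against the stated (1490.7, 1831.7).

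It reproduces. It contains no site, age or baseline term. No efficacy power is stated anywhere.

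**2. Simple size for a linear model on log titre.** If site explains a share R² of the variance and arms are balanced within site, the ratio of adjusted to unadjusted standard error is about √(1 − R²).

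- R² = 0.1: √0.9 = 0.949
- R² = 0.2: √0.8 = 0.894
- R² = 0.3: √0.7 = 0.837

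The standard error falls by 5%, 11% or 16%. These R² values are assumptions, and nothing in the documents supports a particular one.

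**3. NAb simulation.** From the documents: 360 subjects, six sites by two age groups, blocks of 2 or 4, residual log SD 0.70, detection limit 15. Assumed: two sites holding 43% of subjects contain the baseline-positives, whose log titre has mean 7 and SD 1; vaccine effect is additive on baseline log titre. 1000 replicates.

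| Baseline-positive at the two sites | Share overall (0.43 × column 1) | Pooled log SD | SD within site and age | SD with baseline titre added | Size of unadjusted t-test |
|---|---|---|---|---|---|
| 20% | 8.6% | 1.42 | 1.36 | 0.70 | 3.4% |
| 50% | 21.5% | 1.95 | 1.64 | 0.70 | 1.3% |
| 80% | 34.4% | 2.24 | 1.45 | 0.70 | 0.5% |

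With no baseline-positives the t-test size is 5.4% and adjustment gains nothing. Baseline titre matters more than site. The return to 0.70 follows from the assumed model and is not evidence about the trial.

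**4. Does the NAb conclusion depend on this?** If Phase 1 titres recur and placebo sits at 15, then even with a log SD of 2.5:

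z = (7.41 − ln 15)/(2.5 × √(2/180)) = 4.70/0.2635 = 17.8.

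It does not.

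**5. Efficacy simulation.** 400 subjects, the same blocking, 72 weeks of follow-up, 1500 replicates. Site shares, site hazards and the hazard ratio of 0.4 are assumptions. Stratification is by site.

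| Site hazards | Size: unstratified / stratified | Power: unstratified / stratified |
|---|---|---|
| Equal, 2%/yr | – | 20.0% / 20.3% |
| Equal, 5%/yr | – | 46.3% / 46.4% |
| Two sites 15%/yr, rest 1% | 2.9% / 4.0% | 51.9% / 54.6% |
| One site 50%/yr | 1.6% / 5.2% | 62.7% / 76.8% |
| One site 100%/yr | 0.1% / 5.2% | 66.9% / 92.3% |

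Monte Carlo error is about 0.6 points near 5% and 1.3 to 1.6 points near 50%. Stratifying costs nothing visible when sites are alike, gains little under moderate differences, and gains much only when transmission is strongly focal.

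**6. The adjusted analysis is itself inconsistent.** SAP 10.2 names age and site; Tables 15.3.x name age, race and site. In those tables the single-covariate rows use a log-rank stratified by the covariate. The footnote gives the multivariate row a log-rank with no stratification named, so its p-value need not belong to the adjusted Cox estimate beside it.

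**The case against.** For efficacy, the adjusted analysis is already planned: SAP 10.2 and Tables 15.3.x give vaccine efficacy adjusted for site and age, with site-stratified log-rank p-values. Both results will be reported, both are exploratory, and the protocol (6.4.4) declines to rank the case definitions. The order might then seem a matter of taste. This has weight and keeps the point modest. It does not remove it, because the SAP does choose a lead analysis, and the one it chooses ignores the randomisation strata.

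For NAb, SAP 9 calls the summaries descriptive, SAP 5.2 gives the between-arm contrast little weight in sizing the trial, and placebo results may be left out of most summaries if few subjects respond. That stands too. But Table 14.2.1 does carry between-arm p-values, and positive baseline results make an all-negative placebo group less certain.

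Four stronger readings are tempting, and the documents do not support them:

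- *No pooled site-adjusted efficacy estimate exists.* One does, in Tables 15.3.x.
- *The unadjusted estimates are biased by site imbalance.* Allocation is 1:1 in small blocks within site and age, so site is balanced by design. The issue is mainly efficiency and calibration.
- *Transmission is known to differ by site, or baseline antibody was confined to certain sites.* SAP 9 says some sites had positive results. It gives no frequency, titre or comparison with the others, and reports nothing on transmission.
- *The vaccine-versus-placebo NAb finding is at risk.* Step 4 shows that it is not, if Phase 1 titres recur.

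**Conclusion.** The concern holds as a moderate point about efficiency and internal consistency. The rationale in SAP 6.7 does not reach exposure or prior immunity. The lead efficacy analysis and the pooled NAb comparisons leave out factors that the design or data collection already supplies. The direction is conservative: intervals too wide and size below nominal, with no inflation of false positives. The size runs from nil when sites are alike, through a few points of power when two sites carry 15% per year against 1%, to 14 points (62.7% to 76.8%) when one site carries 50% per year. For NAb, the larger gain comes from baseline titre. All of these rest on assumed site hazards, site shares and baseline-positive proportions.

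**What to change.** 1. In SAP 6.7, replace the sentence on centre effects with a statement that sites may differ in exposure and baseline antibody, and that stratification handles this.
2. Where Table 14.2.1 compares arms, compare Week 8 log titre by ANCOVA with baseline log titre, site and age group. Use robust standard errors, because placebo titres may cluster at the detection limit. Compare response rates with a test stratified by site and age group, such as Cochran-Mantel-Haenszel. Keep the unadjusted results as sensitivity analyses.
3. Make the log-rank and Cox analyses stratified by site and age group the lead exploratory efficacy result, with the unadjusted one as sensitivity. State in advance how sparse strata will be collapsed.
4. Use one covariate list in SAP 10.2 and Tables 15.3.x. In the multivariate row, report the p-value from the adjusted Cox model.

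The cost is SAP wording, a few lines of code and revised shells; no new data are needed. The drawback is that strata with few or no cases add little information, which is why the collapsing rule and the unadjusted check are needed.

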6.8 Multiple Comparisons/Multiplicity

This study is not designed to test a specific hypothesis. Rather it is intended to obtain sufficient data to design and implement future efficacy trials. Absent the testing of a formal primary hypothesis there is no requirement for multiple comparison adjustments.

7 STUDY SUBJECTS

7.1 Subject Disposition

Table 14.1.1 (Appendix I), will present a summary of the reasons that subjects were screened but not enrolled.

The composition of analysis populations, including reasons for subject exclusion, by treatment arm, is presented in **Table 14.1.2, Appendix I**.

The disposition of subjects in the study will be tabulated by site and treatment group (**Table 14.1.3, Appendix I**). The table shows the total number of subjects screened, enrolled, receiving at least 1 dose, receiving at least 2 doses, discontinued dosing or terminated from study follow-up and the number completing the study. CHIKV infection status and subject disposition will be tabulated by site and treatment group (**Table 14.1.4, Appendix I**). The table shows the number and percentages of subjects who had a PCR-confirmed CHIKV infection, those with a clinical CHIKV infection (both further split by when infection occurred), and those uninfected.

A flowchart showing the disposition of study subjects, adapted from the CONSORT Statement [3] will be included (**Figure 14.1.1, Appendix II**). This figure will present the number of subjects screened, enrolled, lost to follow-up, and analyzed, by treatment arm where applicable.

A listing of subjects who discontinued dosing or terminated from study follow-up and the reason will be included in **Listing 16.2.1 (Appendix III)**.

7.2 Protocol Deviations

A summary of subject-specific protocol deviations will be presented by the reason for the deviation, the deviation category, and treatment group for all subjects (**Table 14.1.5**). Deviations that are considered major in the categories of ineligibility, product administration, and primary endpoint missing data will be reviewed for possible subject exclusion from the per protocol population. All subject-specific protocol deviations and non-subject-specific protocol deviations will be included in Appendix III as data listings (**Listings 16.2.2.1 and 16.2.2.2, respectively**).

8 SAFETY EVALUATION

8.1 Demographic and Other Baseline Characteristics

Summaries of age, gender, ethnicity, and race will be presented by treatment group overall and by site (**Tables 14.1.6.1-14.1.6.4, Appendix I**). Ethnicity is categorized as Hispanic or Latino, Not Hispanic or Latino, or Unknown/Not reported.

In accordance with NIH reporting policy, subjects may self-designate as belonging to more than one race or may refuse to identify a race, the latter reflected in the eCRF as “No” to each racial option. The race categories to be used are: American Indian or Alaska Native; Asian; Native Hawaiian or Other Pacific Islander; Black or African American; White; Unknown. Individual subject listings (**Appendix III**) will be presented for all demographics (**Listing 16.2.4.1**); pre-existing medical conditions (**Listing 16.2.4.2**); vital signs and oral temperature (**Listing 16.2.9.1**); and concomitant medications (**Listing 16.2.10**).

8.1.1 Concurrent Illnesses and Medical Conditions

All current illnesses and past pre-existing medical conditions will be Medical Dictionary for Regulatory Activities (MedDRA®) coded using MedDRA dictionary version 19.1 or higher.

Summaries of subjects’ pre-existing medical conditions will be presented by treatment group and age stratum (**Table 14.1.7, Appendix I**).

Individual subject listings will be presented for all medical conditions (**Listing 16.2.4.2, Appendix III**).

8.1.2 Prior and Concurrent Medications

Current concomitant prescription medications are recorded in the study database at enrollment. Concomitant medications are updated in the study database if there is an occurrence of an adverse event (AE) that requires expedited reporting. If it will not endanger a subject’s health, non-investigational vaccines should not be administered 14 days before or until at least 28 days after a study injection. Licensed vaccines received by the subject within 4 weeks before the first study injection administration and 4 weeks after last study injection will be recorded in the study database. Otherwise, a record of concomitant medication changes throughout the study will not be recorded in the study database.

All concomitant medications taken during the study will be recorded on the source documentation.

A by-subject listing of concomitant medication for the safety population use will be presented in **Table 14.3.6, Appendix I**.

Individual subject listings will be presented for all concomitant medications (**Listing 16.2.10, Appendix III**).

8.2 Measurements of Treatment Compliance

All subjects were to receive two doses of study product administered in the clinic. The number of doses of study product administered to subjects will be presented by treatment group and by site as part of the subject disposition table (**Table 14.1.3, Appendix I**).

Table 14.1.8 (Appendix I) presents compliance with the dosing schedule, i.e., the number of subjects who received first dose, by treatment arm and by site. **Listing 16.2.5 (Appendix III)** presents individual subject listings for treatment compliance and dosage administration.

8.3 Adverse Events

The severity of an adverse event (AE) is defined as: Grade 1 (Mild), Grade 2 (Moderate), Grade 3 (Severe), Grade 4 (Life-threatening), and Grade 5 (Death). Only the single AE that is assessed as the primary cause of death should be assigned “Grade 5” severity.

Relation of an AE to the study product is defined as Definitely Related, Probably Related, Possibly Related, and Not Related. For purposes of preparing data reports in which AE attributions are limited to “Related” or “Not Related”, in this protocol, the “Definitely, Probably and Possibly” attributions will be mapped to the “Related” category.

AEs will be coded into MedDRA preferred terms.

When calculating the incidence of AEs (i.e., on a per subject basis), each subject will only be counted once and any repetitions of AEs within a subject will be ignored; the denominator will be the total population size. All AEs reported will be included in the summaries and analyses.

